### 1.1 Study design

This is a Phase 2, outcomes assessor-masked, multicenter, randomized study to evaluate the safety and efficacy of two doses of GT005 administered as a single-time subretinal injection in subjects with geographic atrophy (GA) secondary to age-related macular degeneration (AMD).

Approximately 202 subjects are planned to be randomized to GT005 or the untreated control group. Subjects who are screened, but not randomized, will be classed as Screen Failures and will be replaced.

Subjects entered the study must have genotyping and serum Complement factor I (CFI) evaluation performed by a sponsor-approved laboratory, either through participation in a previous Gyroscope sponsored study, or during the EXPLORE screening period. Data from subjects screened in another Gyroscope sponsored study at the same investigative site as EXPLORE may be used to fulfil the screening and eligibility requirements for this study. This is only permissible if the screening data is collected within the screening period specified in the clinical protocol. Should subjects fail to meet the eligibility for EXPLORE, they will be classed as Screen Failures for this study and may be considered for entry into another Gyroscope sponsored study.

Following consent, subjects will undergo ophthalmic and clinical assessments to determine eligibility for inclusion in the study. The consent process and screening assessments will occur at either the subject's local or surgical investigative site. A proportion of the study sites will be designated as centralized surgical sites.

On confirmation of eligibility, subjects in Part 1, will be randomized to one of two dose groups (low dose [ ] vg] or high dose [ ] vg]). Within each part of the study, subjects will be allocated to GT005 or untreated control based on a 2:1 scheme ([Figure 1-1](#)). Once Part 1 enrolment is completed, and the last active subject completes screening and either screen fails or is randomized, then Part 2 can commence. In Part 2, subjects will be randomized to one of two treatment groups (low dose [ ] or untreated control) in a 2:1 scheme.

The eye with the worse visual acuity will be selected as the study eye. If visual acuity is equivalent in both eyes, the eye with the largest area of GA will be the study eye unless the subject (in consultation with the Surgeon) expresses an alternative preference. The study eye will be confirmed by the Vitreoretinal Surgeon.

### **Randomization/Stratification**

Subjects in Part 1 will be randomized to one of two dose groups: low dose ( [REDACTED] vg) or high dose ( [REDACTED] vg). Subjects in Part 2 will be randomized to one of two treatment groups: low dose ( [REDACTED] vg) or untreated control.

[figure not shown]

A permuted-block randomization method will be used to obtain an approximately 2:1 ratio between treatment with GT005 and the untreated control group(s) for each dose group within each stratum ([Figure 1-1](#)).

A treatment assignment will be allocated by Interactive Response Technology (IRT) (additional details will be found in the IRT reference manual provided to each site). Authorized personnel at investigative sites will use the IRT system to randomize subjects. IRT will assign subjects to a treatment code number based on a pre-defined randomization list that will be created by a statistician who is independent from the study.

Upon randomization, subjects will be immediately informed of allocation.

All subjects enrolled must be identifiable throughout the study. The Investigator will maintain a list of subject numbers and names to enable records to be found at a later date if required.

**Figure 1-1** Study Design

Investigational sites can open Part 2 for enrolment once all appropriate approvals for protocol V6.0 are in place (at which point Part 1 is considered closed for enrolment).

GT005 allocated subjects only.

[figure not shown]
The overall objectives of the study are to evaluate the safety and efficacy (anatomical and functional visual outcomes) of two doses of GT005 in genetically defined subjects with GA due to AMD.

## 1.2 Study objectives, endpoints and estimands

**Table 1-1** Objectives and related endpoints

OBJECTIVES	ENDPOINTS
Primary	
• To evaluate the effect of GT005 on the progression of GA in subjects with GA due to AMD	• The change from baseline to Week 48 in GA area as measured by fundus autofluorescence (FAF)
Secondary	
• To evaluate the effect of GT005 on the progression of GA in subjects with GA due to AMD	• The change from baseline through Week 96 in GA area as measured by FAF
• To evaluate the safety and tolerability of GT005	• Frequency of treatment emergent adverse events (TEAE) through Week 96
• To evaluate the effect of GT005 on retinal anatomical measures	• Change in retinal morphology on multimodal imaging through Week 96
• To evaluate the effect of GT005 on functional measures	• Change in best corrected visual acuity (BCVA) Score via the early treatment for diabetic retinopathy (ETDRS) chart through Week 96

- To evaluate the effect of GT005 on visual function
  - Change in low luminance difference (LLD) via the ETDRS chart through Week 96
  - Change in reading performance as assessed by Minnesota low-vision reading test (MNRead) chart through Week 96
  - Change in functional reading independence (FRI) index through Week 96
- To evaluate the effect of GT005 on patient-reported outcomes
  - Change in quality of life measured on the visual function questionnaire-25 (VFQ-25) through Week 96

### 1.2.1 Primary estimand(s)

The primary estimand will focus on the effect attributable to different doses of GT005 on GA change on FAF at Week 48 in subjects who have not received alternative GA medications or therapies in the study eye.

The primary estimand is described by the following attributes:

1. **Population:** Subjects with GA secondary to AMD. Details on the target population are defined by the study inclusion and exclusion criteria.
2. **Variable:** Change from baseline in GA lesion size (mm^2) based on FAF at Week 48
3. **Treatment:** The randomized treatment (different doses) of the investigational therapy GT005 delivered through transvitreal subretinal injection.
4. **Summary Measure:** The treatment difference of the variable means between GT005 and untreated control, represented as % relative to untreated control.
5. **Intercurrent events and data handling strategy:** defined in [Table 1-2](#).

**Table 1-2      Intercurrent Events and Corresponding Primary Data Handling Strategies**

Intercurrent event	Data handling strategy
Subject receives alternative GA medications or therapies in the study eye	GA lesion size data collected in the study eye after the subject initiates alternative GA medications or therapies will be censored and imputed assuming missing at random (MAR)

## 2      Statistical methods

### 2.1      Data analysis general information

The analyses will be performed by the Contract Research Organization (CRO) using SAS 9.4.

Categorical data will be presented as frequencies and percentages. For continuous data, mean, standard deviation, median, minimum, and maximum will be presented. These summary statistics will be presented by the treatment group unless otherwise specified. Where appropriate, point estimates and confidence intervals (CI) of treatment group differences will be provided.

#### 2.1.1      General definitions

##### 2.1.1.1      Study treatment

The following treatment groups will be presented:

- Untreated control
- Low dose GT005 (████ vg)
- High dose GT005 (████ vg)

### 2.1.1.2 Baseline and post-Baseline

*Baseline* (Day 1) is defined as

- the day following randomization for subjects randomized to untreated control
- the day of successfully receiving GT005 administration for subjects randomized to GT005
- or the latest surgery date for subjects who were randomized to GT005 but failed to receive GT005 administration on the first attempt to surgery (if applicable)

The baseline value for efficacy and safety variables is the last available value (scheduled or unscheduled) collected prior to the date of *Baseline*, or on the date of *Baseline* but prior to the time of GT005 administration for GT005 treatment groups.

All data collected after the date of *Baseline* are defined as post-baseline. The *study day* for a baseline or post-baseline scheduled or unscheduled visit is defined as:

$$\text{Study day} = \begin{cases} (\text{Date of visit}) - (\text{Date of randomization}) & \text{Untreated} \\ (\text{Date of visit}) - (\text{Date of treatment administration}) + 1 & \text{GT005} \end{cases}$$

The *study day* for a scheduled or unscheduled visit before baseline is defined as

$$\text{Study day} = \begin{cases} (\text{Date of visit}) - (\text{Date of randomization}) - 1 & \text{Untreated} \\ (\text{Date of visit}) - (\text{Date of treatment administration}) & \text{GT005} \end{cases}$$

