#### 6.1.3.2 Surgery – Day 1 (Surgical Site)

##### Deferred GT005 Delivery

In the event the GT005 administration is deferred during the surgical procedure (e.g., due to an AE occurring during surgery) the administration surgery may be rescheduled within 10 weeks of the original surgery date if agreed by the Sponsor Medical Monitor. Additionally, if the time from screening is extended past 12 weeks, in case of GT005 deferral, FAFs will be repeated, in addition to standard ophthalmic examination, haematology and biochemistry, and visual acuity (BCVA and LLVA).

The following assessments are required during surgery:

- [REDACTED]
- AEs
- Concomitant medications
- [REDACTED]
- [REDACTED]
- [REDACTED]

The procedure for the administration of GT005 is described in Section 5.4 and in the Surgical Manual.

■ [REDACTED]  
■ [REDACTED]  
■ [REDACTED]

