### 7.3.9 Visual Acuity Check

A visual acuity check using a Snellen chart (near card is permissible) must be performed pre-surgery on the study eye if >4 weeks have elapsed between BCVA with ETDRS and surgery. If Snellen result is >2 lines (BCVA equivalent to 10 letters), worse than the previous BCVA ETDRS score, then a BCVA with ETDRS assessment must be repeated. If the BCVA with EDTRS results is  $\leq 2$  lines worsened compared to the previous BCVA with ETDRS, record the subject's vision in the eCRF and surgery can proceed. If the repeat BCVA with EDTRS check remains >2 lines (BCVA equivalent to 10 letters) worsened, surgery must be postponed pending discussion and approval by the Sponsor Medical Monitor.

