### 2.7.3 Loss in best corrected visual acuity

The number and the percentage of subjects who lost  $\geq 15/\geq 30$  letters in BCVA from baseline up to Week 96 will be presented for the study eye and the fellow eye. Missing data will not be imputed.

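### For GT005 subjects re-operated after an aborted first surgery, a BCVA taken between the two operations becomes baseline, so vision lost at the first operation is left out of the BCVA and LLD results

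*SAP*

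**What the plan says.** **Baseline date.** For GT005 subjects, SAP 2.1.1.2 sets Day 1 at "the day of successfully receiving GT005 administration for subjects randomized to GT005". A further rule covers an unsuccessful first operation: "or the latest surgery date for subjects who were randomized to GT005 but failed to receive GT005 administration on the first attempt to surgery". For a subject dosed at a second operation, both rules give the date of that later operation.

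**Baseline value.** "The baseline value for efficacy and safety variables is the last available value (scheduled or unscheduled) collected prior to the date of" Baseline. Only data after that date are post-baseline.

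**Where it is used.** SAP 2.6.2 item 4.a models change from baseline in BCVA with baseline BCVA as covariate, and item 4.b summarises change in LLD. SAP 2.7.3 tabulates subjects losing at least 15 or at least 30 "letters in BCVA from baseline up to Week 96 will be presented for the study eye and the fellow eye". None of these sections gives a different baseline.

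**Second operations.** Protocol 6.1.3.2 foresees dosing being deferred during surgery, with an intra-operative adverse event as its example; "the administration surgery may be rescheduled within 10 weeks of the original surgery date if agreed by the Sponsor Medical Monitor". If the deferral takes the time from screening past 12 weeks, "FAFs will be repeated, in addition to standard ophthalmic examination, haematology and biochemistry, and visual acuity (BCVA and LLVA"). Table 1, footnote 1, separately calls for BCVA/LLVA to be repeated before surgery once the 8-week screening period has elapsed. Protocol 7.3.9 requires a Snellen check when more than 4 weeks separate ETDRS BCVA and surgery, and a repeat ETDRS BCVA if the Snellen result is more than 2 lines (10 letters) worse.

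**The concern.** Protocol 1.6.1.2 names worsening of vision as a risk of the surgical procedure. A subject whose first operation was abandoned and who then had a second has been exposed to that risk twice. When BCVA is measured between the operations, the SAP's rule makes the state of the eye after the first operation the starting point. Loss from the first operation is then absorbed into baseline, and any later recovery from it scores as a gain. Because this can happen only in the GT005 arms, the BCVA comparison with control can be shifted in one direction, in favour of GT005.

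The SAP also treats the same event in two ways. Under 2.7.1 an adverse event counts as treatment-emergent from randomisation, so an event at the aborted operation is on-study harm. The letters lost with it are classed as pre-treatment status.

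**Working it through.** The documents state no figure on this point, so the check applies the baseline rule to cases.

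**1. When is the loss absorbed?** Assume 60 letters before the first surgery, a persistent loss L at that surgery and no later change. The final score is 60 − L. The SAP baseline is 60 − L if there is both a second surgery and an ETDRS BCVA in between; otherwise it is 60.

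| Case | SAP baseline | SAP change | Counted in 2.7.3? |
|---|---|---|---|
| L = 18, one surgery only | 60 | 42 − 60 = −18 | yes, ≥15 |
| L = 18, second surgery, no BCVA between | 60 | 42 − 60 = −18 | yes, ≥15 |
| L = 18, second surgery, BCVA between | 42 | 42 − 42 = 0 | no |
| L = 32, second surgery, BCVA between | 28 | 28 − 28 = 0 | no (would be ≥15 and ≥30) |

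Measured from before the first surgery, the changes are −18 in the first three rows and −32 in the last. Both conditions are needed for absorption. With one surgery only, the latest surgery is the first, so baseline precedes it.

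**2. How likely is a BCVA in between?** The second surgery can fall up to 8 + 10 = 18 weeks after screening, or 12 + 10 = 22 with extended screening. Taking the screening BCVA as the last one before the first surgery, the protocol calls for the following:

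- up to 4 weeks from BCVA to second surgery: no repeat required;
- more than 4 and up to 8 weeks: ETDRS repeat only if Snellen is more than 10 letters worse;
- more than 8 weeks: repeat before surgery (Table 1, footnote 1), and with FAF past 12 weeks (6.1.3.2).

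Unscheduled visits (Protocol 6.1.15) can add values, and the SAP rule admits them. A persistent loss of 15 letters or more that shows on the Snellen check would therefore be re-measured once the second surgery is more than 4 weeks after the last BCVA.

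**3. Smaller losses.** Under 7.3.9, if the repeat ETDRS is no more than 2 lines worse, vision is recorded "in the eCRF and surgery can proceed". Suppose 10 letters are lost at the first operation and re-measured, and 8 more are lost later. The SAP change is 42 − 50 = −8; from before the first surgery it is 42 − 60 = −18, which crosses the 15-letter threshold.

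**4. Effect on the arm mean.** If a share f of an arm is aborted, re-measured and re-operated with mean loss L, the unadjusted mean BCVA change moves by f × L in favour of GT005. Both inputs are assumptions:

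- f = 1%, L = 5: 0.05 letters
- f = 5%, L = 15: 0.75 letters
- f = 10%, L = 30: 3.0 letters

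The last line is a deliberately extreme corner.

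**5. LLD.** LLD is BCVA minus LLVA. Where both are repeated, the change at the first operation is absorbed as well, but its direction depends on which score fell more.

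**The case against.** The strongest reply is that change since actual treatment is a coherent definition, and that little is hidden. All BCVA assessments are listed by subject (SAP 2.6.2, 4.a), as are all unscheduled data (2.1.1.4). Adverse events count from randomisation, with separate tables for procedure-related events (2.7.1). Failed surgeries are summarised by reason and surgical records are listed (2.4.1). Large losses also meet a gate: where the 7.3.9 check applies and repeat ETDRS BCVA is still more than 2 lines worse, surgery is postponed pending Medical Monitor approval. Any rescheduling after deferral needs that monitor's agreement too. Some of these subjects may never be re-operated, and their loss is then counted. The study is exploratory and is being terminated early, so the BCVA model may be run only as data allow.

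All of this stands as a limit on size, and it rules out three stronger readings:

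- A reader might infer that every aborted first surgery erases the vision loss. The first two rows of the case table show otherwise.
- A reader might infer that the loss vanishes from the report. The listings and AE tables keep it.
- A reader might put a percentage on the understated loss rate. That needs the deferral rate and the letters lost, and neither is in the documents.

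The reply does not rescue the summaries themselves. A listing does not correct a table of vision loss. The separate listing of procedure-related AEs covers subjects who did not receive treatment, so it would not pick out someone dosed at the second attempt.

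**Conclusion.** The point holds for one defined group: GT005 subjects re-operated after an aborted first surgery who have an ETDRS BCVA between the operations. For them, vision lost at the first operation drops out of the BCVA-change model and the 15-/30-letter loss table. The LLD change summary is affected too where LLVA was repeated. For BCVA the error favours GT005 and cannot occur in controls.

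The group is probably small. The shift of 0.05 to 3.0 letters in the arm mean rests wholly on assumed f and L and is a range of possibilities, not an estimate. The defect in the definition does not depend on it. It is worth correcting because it is one-sided and bears on a surgical safety result.

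The point does not extend to all safety variables. Nothing in the documents argues for moving the reference for laboratory values or vital signs back to before the first operation.

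**What to change.** In SAP 2.1.1.2, add that for study-eye BCVA and LLVA/LLD the baseline value is the last value before the first study surgery attempt, whether or not GT005 was then given. Use it in 2.7.3 and in 2.6.2 items 4.a and 4.b. If the present definition is kept as the main one, show the alternative at minimum as a sensitivity display. Report by treatment group how many subjects had more than one surgical attempt, and how many of those had a BCVA in between. Keep the present rule for GA area, laboratory values, vital signs and visit timing.

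The cost is one SAP sentence and a derivation from surgery dates and BCVA/LLVA scores already collected. The downside is that BCVA and GA area would have different baseline dates in these few subjects, which a footnote can state.

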### 2.1.1.3 End of study mapping

The end of study date is the date when a subject completes or discontinues the study. For reporting data by visit in outputs, the end of study visit will be allocated to the actual (reported) visit number. If the end of study date is not on a scheduled visit, then the end of study visit will be allocated, based on study day, to the closest future scheduled study visit.

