#### **STATISTICAL METHODS:**

### Sample Size and Statistical Power

Untreated control mean GA change at 48 weeks was assumed to be 2.1 mm^2 with SD=1.3 mm^2. Up to ~10–12% of subjects are expected to discontinue treatment and not provide the target 48 week observation.

[REDACTED]

[REDACTED]

[REDACTED]

[REDACTED]

[REDACTED]

[REDACTED]

[REDACTED]

[REDACTED]

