### 2.1.1.4 Unscheduled visits

For unscheduled visits, the analysis visits will be derived with windowing where appropriate (e.g., Visit  $3 \pm 3$  days) as per the protocol. For scheduled visits, the analysis visits will be the actual (reported) visit number.

Data collected at unscheduled visits will not be used in 'by-visit' tabulations, graphs or analyses unless it can be mapped to a missed scheduled visit with the window specified per the protocol. If multiple unscheduled visits are allocated to the same missed scheduled visit:

- The unscheduled visit closest to the missed scheduled visit will be used
- If there are multiple unscheduled visits with the same distance to the missed scheduled visit, the latest one will be used

For analyses showing abnormalities, data from unscheduled visits will be considered individually, without mapping to a main visit.

For analyses based on all post-baseline values such as averages over a given period summaries of maximum/minimum values, data collected at unscheduled visits will be included.

All data collected at unscheduled visits will be listed.

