### **2.1.1.5 Missing baseline and post-baseline data**

Missing baseline data will not be imputed.

Observations with values ‘not done’, ‘not evaluable’, ‘not applicable’ will be treated as missing values.

In case of multiple entries for the same assessment are observed within one visit, the latest assessment value will be used.

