### **2.5.4 Handling of missing values not related to intercurrent event**

In the case of missing data occurring in other scenarios, i.e. independent of intercurrent events defined in [Table 1-2](#), the estimand based on an MAR approach will be considered specifically for each treatment arm the subjects are assigned.

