### 5.4 Statistical models

#### 5.4.1 Analysis supporting primary objective(s)

The following MMRM will be used for the primary efficacy endpoint. The model will include the change from baseline in GA area measured by FAF as the dependent variable, GA area at the baseline as the covariate, assessment visit, treatment group, two interaction terms (assessment visit and treatment group, assessment visit and GA area at the baseline) as the fixed effect and participant as a random effect.

For this analysis, the data structure is one record per subject per scheduled visit. The data will include all subjects and have records for all scheduled visits, regardless of whether the assessment was missed or not at a given visit. Missing values will not be imputed and will be passed to the model as missing. The SAS PROC MIXED will be used to perform the analysis.

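### The SAP moves an off-schedule end-of-study visit forward to the next scheduled visit with no window, so a GA area can be labelled Week 48 up to about 12 weeks early, or Week 72 or 96 up to about 24 weeks early

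*SAP*

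**What the plan says.** SAP 2.1.1.3 (End of study mapping) keeps the reported visit number where there is one. If the end-of-study date is not on a scheduled visit, "the end of study visit will be allocated, based on study day, to the closest future scheduled study visit". It gives no window, and it does not say whether a date within ±7 days counts as on schedule.

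SAP 2.1.1.4 (Unscheduled visits) bars unscheduled data from by-visit tables, graphs and analyses "unless it can be mapped to a missed scheduled visit with the window specified per the protocol". Protocol Tables 1 and 2 set that window at ±7 days for Weeks 12 to 96. Protocol 6.1.14 includes FAF at the Early Termination Visit.

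For the model, SAP 5.4.1 states that "the data structure is one record per subject per scheduled visit" and "Missing values will not be imputed and will be passed to the model as missing". SAP 2.5.4 adds that, for missing data unrelated to the intercurrent event, "the estimand based on an MAR approach will be considered specifically for each treatment arm". SAP 2.5.5 and 2.5.6 plan no sensitivity or supplementary analysis.

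**The concern.** The same off-window FAF image is kept out of by-visit output if it comes from an unscheduled visit, but given a later visit's label if it comes from the exit visit. GA area grows, so the relabelled value understates growth at the visit it is assigned to. It usually fills a cell that 2.5.4 and 5.4.1 would otherwise leave missing under MAR.

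By-visit tables follow the mapping directly. The MMRM is not named in 2.1.1.3. However, that section is a general definition, the model takes one record per scheduled visit, and no term carries actual time. Entry into the MMRM is therefore a strong inference.

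Off-schedule exits are foreseeable. SAP Section 1 says that the study is being terminated early, and after Week 48 the visits are 24 weeks apart. At stake are the level of the arm means and the mm² differences, mainly at Weeks 72 and 96.

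**Working it through.** The plan gives no figure for this rule, so there is none to reproduce.

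**Inputs.** Visits at Weeks 12, 24, 36, 48, 72 and 96 with a ±7-day window (Protocol Tables 1 and 2). Control mean change 2.1 mm² at 48 weeks, SD 1.3 (Protocol 9.1, SAP 3). Up to about 10-12% of subjects "expected to discontinue treatment and not provide the target 48 week observation" (Protocol synopsis). Assumptions: linear growth, exits spread evenly, and the same weekly exit rate after Week 48.

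**1. Rate.** 2.1/48 = 0.04375 mm² per week, so expected growth is 2.10, 3.15 and 4.20 mm² at Weeks 48, 72 and 96.

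**2. Largest shift for one record** (weeks early × rate; % of expected growth).

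| Label | ±7 days counts as on schedule | No tolerance |
|---|---|---|
| Week 48 | 11 wk: 0.48 mm² (23%) | 11.86 wk: 0.52 mm² (25%) |
| Week 72 | 23 wk: 1.01 mm² (32%) | 23.86 wk: 1.04 mm² (33%) |
| Week 96 | 23 wk: 1.01 mm² (24%) | 23.86 wk: 1.04 mm² (25%) |

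**3. Raw arm means at the planned loss** (share of records moved × average proportional shift).
- Week 48: 10% × 10/48 to 12% × 12/48 = 2.1-3.0% of subjects, or 2.3-3.3% of Week 48 records. Average shift 6/48 = 12.5%. The mean is 0.28-0.41% low.
- Week 72: 22 off-window weeks give 5.1-6.3% of records. Average shift 12/72 = 16.7%. The mean is 0.85-1.05% low.
- Week 96: 5.4-6.7% of records. Average shift 12/96 = 12.5%. The mean is 0.68-0.84% low.

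Simulation agrees: about 0.2-0.4%, 0.7-1.0% and 0.5-0.8%.

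**4. MMRM means.** These were simulated with linear subject slopes, SD about 1.3 at Week 48, residual SD 0.2 or 0.6, and baseline GA area as covariate (mean 8, SD 3.5, correlation about 0.3 with slope). The residual SDs and covariate values are assumed. Exits before Week 36 matter here. Their values are relabelled Week 24 or 36, the subject looks like a slow grower, and the model carries that forward. Counting them, the means are roughly 1-2%, 1.5-3% and 1.5-3% low at Weeks 48, 72 and 96. Ignoring them gives only 0.3-0.4% at Week 48. Under the window rule the means stay within about 0.1%.

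**5. Against sampling error.** Take 64 subjects in an arm, (202 − 10)/3. The SE is 1.3/8 = 0.16 mm² at Week 48. If SD grows with time, it is 1.95/8 = 0.24 at Week 72 and 2.6/8 = 0.33 at Week 96. The biases in step 4 are 0.02-0.04, 0.05-0.09 and 0.06-0.13 mm². Simulated RMSE was about the same under either rule.

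**6. If exits are many.** With 30% off-window at each visit (assumption), simulated RMSE at Week 48 is 0.175 with forward mapping and 0.164-0.177 with the window rule. It falls from 0.31-0.32 to 0.25-0.26 at Week 72 and from 0.45-0.46 to 0.33-0.36 at Week 96.

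**7. A bound from the dates.** Part 2 could not open before protocol V6.0 (6 December 2022), 414 days or 59.1 weeks before the SAP date (24 January 2024). If Part 2 subjects left by the SAP date (assumption; exit dates are not given), any Part 2 value labelled Week 72 is at least 72 − 59.1 = 12.9 weeks early. That is 0.56 mm², or 18% of 3.15.

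**The case against.** **The two sections govern different things.** Early termination is a protocol visit with its own assessment column, so a separate rule for it is a convention and not a contradiction. That stands. The point is the consequence of the rule. The move is also not unlimited, because the next visit caps it.

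**The effect is small at the only loss rate in the documents.** This stands too. The 23-33% figures are worst cases for one record, and the arm-level biases are well below the SE.

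**No bias in the treatment comparison is shown.** A reader might infer that the rule favours GT005, since treated subjects move to the follow-up study. The documents do not support that. The estimand's summary is "represented as % relative to untreated control", and on that scale equal proportional shrinkage cancels. Bias needs a different share or timing of off-schedule exits between arms, which is not documented. One structural difference exists: the high-dose group is about 10 Part 1 subjects, while the pooled control also includes Part 2. If 10% of control records were moved and none in the high-dose arm, the high dose would show false excess growth of 1/(1 − 0.0125) − 1 = 1.3% at Week 48 and 1/(1 − 0.0167) − 1 = 1.7% at Week 72. With 10 subjects the SE is 1.3/√10 = 0.41 mm², about 20% of 2.1, so a shift of that size would not be visible.

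**Discarding the last FAF may hurt MAR if fast progressors leave early.** This is a fair point. In a simulation with faster growers leaving earlier, MMRM means were about 2% low under the window rule, against 3-5% low with forward mapping. The window rule is not free of bias there, but it has less.

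**The records are already listed.** SAP 2.3.1 lists discontinuations and 2.6.2 lists all GA assessments. The listings show individual cases, but no planned analysis measures the effect. Modelling depends on data availability (2.5.2), yet by-visit summary tables would use the same mapping.

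**Some cases are harmless.** Visits reported under a scheduled number are unaffected. An exit days after an early in-window visit falls under 2.1.1.5: "In case of multiple entries for the same assessment are observed within one visit, the latest assessment value will be used".

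**Conclusion.** The point holds in a limited form. The rule as written labels early GA areas as later visits, by up to about 0.5 mm² per record at Week 48 and 1.0 mm² at Weeks 72 and 96 (planned growth, assumed linear). At the planned loss, extended at the same rate after Week 48, raw arm means are at most about 1% low. MMRM means are roughly 1-3% low under the assumed residual SDs, provided the mapping feeds the model. The direction is certain for growing lesions, but the number of affected records is not in the documents.

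Three stronger readings are not supported. The Week 48 arm mean is not off by a quarter. No distortion of the GT005 comparison is shown. The window rule is not shown to be more accurate overall at planned loss rates: it removes bias without improving RMSE. A net gain needs many off-window exits, which early termination makes plausible but the documents do not quantify. The point merits a text change before lock and does not by itself put the study's conclusions in doubt.

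**What to change.** In SAP 2.1.1.3, for the GA-area by-visit summaries and the MMRM only, use an off-schedule end-of-study or early-termination FAF only if it falls inside the protocol window of a missed scheduled visit, as 2.1.1.4 already does for unscheduled visits. Otherwise list the value and leave that visit missing under MAR (2.5.4, 5.4.1). State whether a date inside the window counts as on schedule. Report the number of off-window end-of-study FAF records by arm and by study part, so that any imbalance can be seen.

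The cost is one sentence of SAP text and a visit-mapping change before final lock. There would be fewer late observations, and a late visit may become too sparse to model. The SE of an arm mean of 64 rises by 0-2% at the planned loss, and by about 3-13% if 30% are off-window at each visit (assumption). Limiting the change to GA area leaves the handling of other endpoints as it is.
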